7. ASSESSMENTS

Every effort should be made to ensure that the protocol required tests and procedures are completed as described. However it is anticipated that from time to time there may be circumstances, outside of the control of the investigator that may make it unfeasible to perform the test. In these cases the investigator will take all steps necessary to ensure the safety and well being of the subject. When a protocol required test cannot be performed the investigator will document the reason for this and any corrective and preventive actions which he/she has taken to ensure that normal processes are adhered to as soon as possible. The study team must be informed of these incidents in a timely fashion.

7.1. Safety Assessments

For subjects in the active treatment period, and the withdrawal/re-treatment period, safety will be assessed using the following measures:

1. Physical examinations will be performed by a physician. Any clinically significant abnormalities or worsening of medical history conditions should be recorded on the source documents and the appropriate adverse event CRF.
 - The physical examination will include the Tanner Stage Assessment for subjects <18 years of age or who have a score of <5 on 1 or more applicable domain(s). The sexual maturity rating of each subject will be determined according to the criteria adapted from Tanner. Female subjects will be classified on a scale of 1 to 5 across the following 2 maturity domains: breast and pubic hair characteristics. Male subjects will be classified on a scale of 1 to 5 across the following 3 maturity domains: pubic hair, penis and testes characteristics.
2. Vital sign measurements will include temperature, blood pressure and pulse rate (after sitting for at least 5 minutes).
 - A sitting blood pressure will be obtained by qualified site personnel and should be taken using the same arm throughout the study. If possible, a different arm should be used for the collection of blood samples.
3. Height and Weight.
4. Subjects will be evaluated for adverse events (infectious and noninfectious), serious adverse events, malignancy, and medically important infections.

- Infectious and noninfectious adverse events will be recorded on separate CRFs.
 - Medically important infections are defined as infections that require parenteral anti-infective agents (IV, IM) and/or hospitalization.
 - Infections considered preventable by vaccination will be reported on the infectious adverse event CRF.
5. Injection site reactions (symptoms, action taken, number, and frequency) will be monitored throughout the study and will be graded for intensity according to the Symptom Occurrence Scale (Itching, Redness, Swelling, Pain, Ulceration). Injection site reactions need to be clearly differentiated from symptoms associated with the technique of administering subcutaneous injections (eg, physical injury to blood vessels).
6. Clinical laboratory evaluations including blood chemistry, hematology, and urinalysis.

For subjects in the observational period, safety will be assessed through collection of the following information via telephone contact:

1. Subjects will be evaluated for serious adverse events, malignancy, and medically important infections.
 - Infectious and noninfectious serious adverse events will be recorded on separate CRFs.
 - Medically important infections are defined as infections that require parenteral anti-infective agents (IV, IM) and/or hospitalization.

7.2. Laboratory Evaluations

As much as possible, only one laboratory will be used by each investigator for all determinations. Laboratory certification and laboratory normal ranges must be provided to the sponsor for all laboratories used, excluding the laboratory ranges and certifications for the sponsor designated central laboratory.

All laboratory tests with values that become abnormal to a clinically significant degree after investigational product administration must be repeated and the investigator must continue to follow up as medically indicated until values have returned to baseline or until the condition stabilizes. If laboratory values do not return to normal or baseline within a reasonable period, the etiology must be identified and the sponsor notified. In the judgment of the investigator, all clinically significant abnormal laboratory tests will be recorded on the appropriate adverse event CRF. In addition, additional laboratory testing may be performed according to local guidelines or standard of care and for follow-up of abnormal laboratory test results.

Sample collection, storage, and shipping information can be found in the laboratory manual supplied by the sponsor designated central laboratory. Laboratory evaluations will include the following:

1. Pregnancy test (performed locally with material provided by the central laboratory): For female subjects, who in the opinion of the investigator are biologically capable of having children, a urine pregnancy test must be performed within 7 days prior to the baseline (day 1) visit and at each of the visits in the active treatment period during the withdrawal/re-treatment period, including the early withdrawal visit(s) and the re-treatment assessment visit; this includes subjects who are menstruating at the time of the visit. A negative urine pregnancy test must be obtained prior to administration and dispensing of investigational product at each of the visits in the active treatment period and the re-treatment period. Pregnancy tests will also be done whenever one menstrual cycle is missed during the active treatment period and withdrawal/re-treatment period or when potential pregnancy is otherwise suspected. Pregnancy tests may also be repeated as per request of IRB/IECs or if required by local regulations.
2. Serum chemistry: alkaline phosphatase, alanine aminotransferase (ALT)/serum glutamic pyruvic transaminase (SGPT), aspartate aminotransferase (AST)/serum glutamic oxaloacetic transaminase (SGOT), and total bilirubin.
3. Hematology: white blood cell (WBC) count including differential, red blood cell (RBC) count, hemoglobin, and platelet count.
4. CRP evaluation.
5. Evaluation of potential Hy's Law cases: Repeat testing will include AST, ALT, albumin, creatine kinase, total bilirubin, direct and indirect bilirubin, gamma-glutamyl transferase (GGT), prothrombin time (PT)/international normalized ratio (INR), and alkaline phosphatase. At the discretion of the investigator, additional testing for acute hepatitis A, hepatitis B, or hepatitis C may also be performed at the site's local laboratory.

7.3. Efficacy Assessments

For subjects in the active treatment period, and in the withdrawal/re-treatment period, efficacy will be assessed.

1. The following assessments will be completed by the subject's parent or legal representative/guardian for subjects aged <18 years; these will be completed directly by subjects aged ≥18 years at the time of the assessment.
 - Patient/Parent Global Assessment: The subject or parent will assess all the ways that arthritis affects the subject using a scale between 0 and 10 on a 21-circle VAS with 0 = Very Well and 10 = Very Poor. This is to be completed in a manner that does not bias the investigator's assessment of the subject.

- Pain Assessment: The subject or parent will assess how much pain the subject has had because of his/her illness in the past week (0-10 on a 21-circle VAS with 0= no pain and 10=very severe pain). The Pain Assessment should be completed before the joint assessment.
 - Duration of morning stiffness: Based on the investigator questioning the subject or parent, the time elapsed when the subject awoke in the morning and was able to resume normal activities without stiffness will be provided in minutes and cannot exceed 1440 minutes within 24 hours; If morning stiffness was continuing at the time of assessment or was unusual compared to the recent past, the average duration of stiffness over the past 3 days should be reported.
 - Overall Back Pain and Nocturnal Back Pain ([0-100 mm VAS with 0= no pain and 100= most severe pain], ERA subjects only).
2. PGA of Disease Activity: The investigator will estimate the subject's overall disease activity for the current day by using a scale between 0 and 10 on a 21-circle VAS with 0 = No Activity and 10 = Maximum Activity. This is to be completed in a manner that does not bias the Patient/Parent Global Assessment
 3. Number of active joints, defined as joints with swelling or, in the absence of swelling, joints with limitation of motion with pain and /or tenderness. Joint assessors will assess 68 joints for swelling, 69 joints for limitation of motion, and 75 joints for pain and/or tenderness on motions as follows: 0=no swelling, limitation of motion, or pain and/or tenderness on motion; 1=any swelling, limitation of motion, or pain and/or tenderness on motion; JR = joint replacement; NE=not evaluable
 4. Number of joints with limited range of motion. Joint assessors will assess 69 joints for limited range of motion as follows: 0=no limited range of motion; 1=any limited range of motion; JR = joint replacement; NE=not evaluable
 5. Laboratory measure of inflammation (CRP)
 6. BASMI consists of 5 clinical measurements to reflect axial status (ERA subjects only):
 - Intermalleolar Distance: The subject should lie supine with the knees straight and feet pointing straight up. The subject is asked to separate the legs as far as possible and the distance between the medial malleoli is measured (in cm to the nearest tenth of a cm). Measure two tries.
 - Cervical Rotation: The subject should be in the neutral position. The subject is then asked to turn the head as far as possible to the right and then to the left. Use a inclinometer to measure two tries on the right side and two tries on the left side in degrees (to the nearest degree).
 - Modified Schober's Test: With the subject standing erect, place a mark in the midpoint of a line that joins the posterior superior iliac spines (baseline mark).

Place another mark 10 cm above the first (baseline mark). Then, have the subject maximally bend forward, keeping the knees fully extended. With the subject's spine in full flexion, re-measure the distance between the two marks. The full measurement between the two lines should be recorded to the nearest tenth of a centimeter.

- **Lateral Flexion:** The subject should stand as close to the wall as possible with shoulders level and outer edges of feet 30 cm apart and feet parallel (neutral position). The distance between the subject's middle fingertip and the floor is measured in cm (to the nearest tenth of a cm). The patient is asked to bend sideways without bending the knees or lifting the heels while attempting to keep the shoulders in the same place (flexion position). The distance between the subject's middle fingertip and the floor is re-measured. Measure two tries on the right side and two tries on the left side.
 - **Tragus to Wall Distance:** Place the subject standing with his/her back against the wall; knees straight; scapulae, buttocks, and heels against wall; and head in as neutral position as possible. Measure the distance between the tragus and wall in cm (to the nearest tenth of a cm) from both the right side and left side. Measure two tries on the right side and two tries on the left side.
7. BSA will be measured as the percentage of BSA affected by psoriasis using the palm method; the subject's palm will be used for the calculation, with 1 of the subject's palms to PIP and thumb equal to 1% of BSA (PsA subjects only).
 8. PGA of Psoriasis will assess the amount of induration, erythema, and scaling averaged over all psoriatic lesions on a scale of 0-5 (PsA subjects only).

7.4. Health Outcome Assessments

Health outcomes will be assessed using the CHAQ and HAQ.

The CHAQ will be completed by the subject's parent or legal representative/guardian for subjects aged <18 years at the time of the assessment; HAQ will be completed directly by subjects aged ≥18 years at the time of the assessment.

The health outcomes assessments (ie, CHAQ/HAQ) are for the purpose of exploring the subject's own perceptions about his/her quality of life. The investigator must not influence the subject's assessment. Every effort should be made by site personnel to maintain an unbiased assessment.

7.4.1. Childhood Health Assessment Questionnaire (CHAQ)

The CHAQ, derived from the adult HAQ, is a parent-administered, reliable and valid assessment of functional disability and discomfort in pediatric subjects with rheumatic diseases. The parent of the pediatric subject is asked to report the subject's ability to perform activities of daily living, over the past week, in the following eight domains: dressing, arising, eating, walking, hygiene, reach, grip, and common activities distributed among a

total of 30 items. Each item within a domain is scored on a 4-point Likert scale from 0 to 3: 0=no difficulty; 1=some difficulty; 2=much difficulty; 3=unable to do. Not Applicable is also included as an option. The highest score reported for a domain determines the score for that domain. If aids or devices are used, or assistance is required, the minimum score for that functional area is 2. The Disability Index is calculated as the mean of the eight functional areas.¹⁹ The English version of the CHAQ is included in [Appendix 2](#). The appropriate language form will be used for each participating country.

7.4.2. Health Assessment Questionnaire (HAQ)

The HAQ assesses the degree of difficulty a subject has experienced during the past week in 8 domains of daily living activities: dressing and grooming, arising, eating, walking, hygiene, reach, grip, and other activities. Each activity category consists of 2-3 items. For each question in the questionnaire, the level of difficulty is scored from 0-3 with 0 representing “no difficulty,” 1 as “some difficulty,” 2 as “much difficulty,” and 3 as “unable to do.” Any activity that required assistance from another individual or requires the use of an assistive device adjusts to a minimum score of 2 to represent a more limited functional status. The English version of the HAQ is included in [Appendix 3](#). The appropriate language form will be used for each participating country.

8. ADVERSE EVENT REPORTING

8.1. Adverse Events

All observed or volunteered adverse events regardless of treatment group or suspected causal relationship to the investigational product(s) will be reported as described in the following sections.

For all adverse events, the investigator must pursue and obtain information adequate both to determine the outcome of the adverse event and to assess whether it meets the criteria for classification as a serious adverse event requiring immediate notification to Pfizer or its designated representative. For all adverse events, sufficient information should be obtained by the investigator to determine the causality of the adverse event. The investigator is required to assess causality. Follow-up by the investigator may be required until the event or its sequelae resolve or stabilize at a level acceptable to the investigator, and Pfizer concurs with that assessment.

As part of ongoing safety reviews conducted by the Sponsor, any nonserious adverse event that is determined by the Sponsor to be serious will be reported by the Sponsor as an SAE. To assist in the determination of case seriousness further information may be requested from the investigator to provide clarity and understanding of the event in the context of the clinical study.

8.2. Reporting Period

For SAEs, the active reporting period to Pfizer or its designated representative begins from the time the subject provides informed consent, which is obtained prior to the subject’s participation in the study, ie, prior to undergoing any study-related procedure and/or

receiving investigational product, through at least 96 months after the baseline visit in study B1801023. In addition, for subjects who are either in the active treatment period or the re-treatment period at Month 96, serious adverse events will be collected until 30 days after the last dose of investigational product. SAEs occurring to a subject after the active reporting period has ended should be reported to the Sponsor if the investigator becomes aware of them; at a minimum, all SAEs that the investigator believes have at least a reasonable possibility of being related to investigational product are to be reported to the Sponsor.

AEs (serious and nonserious) should be recorded on the CRF from the time the subject enters either the active treatment period or withdrawal/re-treatment period at the baseline visit of study B1801023 through the subject's last visit in the active treatment period and/or the withdrawal/re-treatment period of the study and for 30 days after the last dose of investigational product for those subjects who are in either the active treatment period or the re-treatment period at Month 96.

For subjects in the active treatment period:

All adverse events (serious and non-serious), including infections, medically important infections, injection site reactions, and malignancy must be recorded on the CRF from the time the informed consent is signed through the Month 96 visit or upon early withdrawal from the study. All adverse events will be collected for the duration of the active treatment period and for 30 days after the last dose of investigational product for those subjects who are either in the active treatment period or the re-treatment period at Month 96.

Events reported as ongoing at the final study 0881A1-3338 visit as well as events starting between the final study 0881A1-3338 visit and baseline visit of study B1801023 must also be recorded on the appropriate CRF.

For subjects in the withdrawal/re-treatment period:

All adverse events (serious and non-serious), including infections, medically important infections, injection site reactions, and malignancy must be recorded on the CRF from the time the informed consent is signed through the duration of the withdrawal/re-treatment period. All adverse events will be collected for the duration of the withdrawal/re-treatment period and for 30 days after the last dose of investigational product for those subjects who are in either the active treatment period or the re-treatment period at Month 96.

For subjects entering directly into the withdrawal/re-treatment period at the baseline visit of study B1801023, events reported as ongoing at the final study 0881A1-3338 visit as well as events starting between the final study 0881A1-3338 visit and baseline visit of study B1801023 must also be recorded on the appropriate CRF.

For subjects in the observational period:

All serious adverse events (including serious infections), malignancy and medically important infections must be recorded on the CRF from the time the informed consent is signed or when the subject enters the observational period through the Month 96 visit.

For subjects entering into the observational period at the baseline visit of study B1801023, events reported as ongoing at the final study 0881A1-3338 visit as well as events starting between the final study 0881A1-3338 visit and baseline visit of study B1801023 must also be recorded on the appropriate CRF.

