- c. Subjects in the active treatment period of study B1801023 who withdraw from investigational product before completion of the month 96 visit are required to complete the early withdrawal visit at the study site. Subjects in the active treatment period who meet Wallace definition for clinically inactive disease for at least 6 months on investigational product or who, in the investigators judgment, have had a good clinical response and would benefit from withdrawal from investigational product and are otherwise eligible will be asked to participate in the withdrawal/re-treatment period. Subjects in the active treatment period who are ineligible for the withdrawal/re-treatment period will be asked to participate in the observational period.
- d. The follow-up visit will only be completed for those subjects who are receiving investigational product in either the active treatment period or re-treatment period approximately 96 months after the baseline visit in study B1801023 and will occur 30 days (± 7 days) after the Month 96 visit.
- e. Subjects who receive at least 1 dose of investigational product in the active treatment period of study B1801023 and withdraw from the active treatment period before completion of the month 96 visit and do not participate in the withdrawal/re-treatment period will be asked to participate in the observational period.
- f. For subjects who consent to participate in the observational period, the first observational visit will occur at the study site and will be scheduled 30 days (± 7 days) after the early active treatment withdrawal visit.
- g. Subsequent observational visits will occur by telephone every 6 months (± 4 weeks) after the first observational visit. For subjects < 18 years of age, telephone contacts will be conducted with the subject's parent or legal representative/guardian. For subjects aged ≥ 18 years, telephone contacts will be conducted with the subject or the subject's parent or legal representative/guardian. The number of telephone contacts will be adjusted based on when the subject enters the observational period.
- h. The final observational visit will occur by telephone contact 96 months (± 4 weeks) after the baseline visit of study B1801023.
- i. For subjects in the active treatment period, the following concomitant medications will be collected: DMARDs, corticosteroids, NSAIDs, and anti-infective agents. Only non-drug treatments received due to an adverse event will be collected.

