- s. Adverse events will be collected from the signing of the informed consent document through 96 months after the baseline visit of study B1801023. For subjects who complete the Month 96 visit in either the active treatment period or the re-treatment period of study B1801023, adverse events will be collected until 30 days after the last

dose of investigational product. Events reported as ongoing at the final study 0881A1-3338 visit as well as events starting between the final study 0881A1-3338 visit and the baseline visit of study B1801023 must be recorded on the appropriate eCRF.

- ^t. For subjects in the active treatment period, all adverse events, malignancies, serious adverse events, infections, medically important infections (ie, an infection requiring parenteral [IV, IM] anti-infective agent(s) and/or hospitalization), and injection site reactions, will be collected.
- ^u. For subjects in the observational period, only serious adverse events, malignancies and medically important infections (ie, an infection requiring parenteral [IV, IM] anti-infective agent(s) and/or hospitalization), will be collected.

Abbreviations: CHAQ=Childhood Health Assessment Questionnaire; DMARD=Disease-Modifying Antirheumatic Drug; eCRF=electronic Case Report Form; HAQ=Health Assessment Questionnaire; IRB=Internal Review Board; IWR/IVR=interactive web response/interactive voice response; NSAID= Nonsteroidal Anti-inflammatory Drug; PGA=physician's global assessment; TNF=tumor necrosis factor

SCHEDULE OF ACTIVITIES – WITHDRAWAL PERIOD

For subjects who enter into the withdrawal period in study B1801023

The Schedule of Activities table provides an overview of the protocol visits and procedures. Refer to Study Procedures ([Section 6](#)) and Assessments ([Section 7](#)) for detailed information on each procedure and assessment required for compliance with the protocol.

Protocol Activity	Withdrawal Period						Observational Period ^e		
	Day 1 ^a Baseline	Months 1 ^b ,3,6,9	Months 12, 24, 36, 48, 60, 72, 84 ^c	Months 18, 30, 42, 54, 66, 78, 90 ^c	Month 96 ^c	Re-Treatment Assessment ^d	1 st Visit ^f	Subsequent Visits ^g	Final Visit (Month 96) ^h
Informed Consent/Assent for Withdrawal/Re-treatment Period	X					X			
Review Inclusion and Exclusion Criteria for Withdrawal/Re-treatment Period	X								
Collect/update contact information	X	X	X	X	X		X	X	
Prior and concomitant medications/non-drug treatments	X ⁱ	X ⁱ	X ⁱ	X ⁱ	X ⁱ	X ⁱ	X ^j	X ^j	X ^j
Height (cm)	X ^a		X	X	X	X			

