6.1.3. Active Treatment Period Follow-up Visit

The follow-up visit will only be completed for subjects who are receiving investigational product in either the active treatment period or the re-treatment period approximately 96 months after the baseline visit in study B1801023. The follow-up visit will occur at the study site 30 days (± 7 days) after the month 96 visit.

The following information will be collected at the follow-up visit:

1. Concomitant medications (DMARDs, corticosteroids, NSAIDs, and anti-infective agents) and non-drug treatments received due to an adverse event.
2. Adverse events, including malignancies, serious adverse events, infections, medically important infections, and injection site reactions.
3. Complete the End of Study Subject Summary CRF.

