4.2.2. Secondary Endpoints

The secondary endpoints include

- *the occurrence of serious adverse events (SAE, infectious and non-infectious events will be summarized separately),*
- *the occurrence of medically important infections (ie, an infection requiring hospitalization and /or parenteral [intravenous (IV), intra-muscular (IM)] anti-infective agents).*
- Hospitalization: For any hospitalizations, the admission date, discharge date and reason for hospitalization will be collected during the study.
- Death: For any deaths, date of death and cause of death will be collected during the study.

- Nonstudy medication: nonstudy medications are coded using the WHO Drug Dictionary (2006 Q3). The Prior, Concomitant, After (PCA) flag for nonstudy medications will be derived for both parent study and extension study (only for active treatment period):
 - Prior nonstudy medications are defined as any nonstudy medications taken before the first dose of investigational product taken at the start of the study,
 - Concomitant nonstudy medications are defined as any nonstudy medications taken during the treatment period (from the first dose to the last dose of the investigational product).
 - After nonstudy medications refer to any nonstudy medications taken after the last dose of the investigational product.(not applicable for observational period)
- Exposure: the total number of doses taken and exposure time.

The above endpoints will be collected for all subjects. The following endpoints will be collected only for subjects in the active treatment period, or withdrawal/re-treatment period in the extension study:

Non-serious adverse Events (Adverse events that occur up to 30 days after the last dose of investigational product will be counted as having occurred during the treatment period) This is applied for active and retreatment periods. If an AE started in active or retreatment period and continued into withdrawal or observational period, it will be only counted in active or retreatment period, it will not be counted in withdrawal or observational period again. If an event started in withdrawal or observational period, and after 30 days of the last dose of investigational product of active period or re-treatment period, this event will not be counted.

Occurrence of withdrawals from investigational product due to adverse events;

Laboratory evaluations (ie, hematology, blood chemistry, and CRP)

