5.2. Treatment-emergent Events

An event is defined as a treatment-emergent event if the event occurred during the active period (either parent or extension studies) or re-treatment period with onset dates between the first dose date of investigational product and within 30 days after the last dose of investigational product. If a treatment-emergent event started in active or re-treatment period and continued to withdrawal or observational period, it will be only counted in active or re-treatment period, it will not be counted in withdrawal or observational period again. If an event started in the withdrawal or observational periods, and after 30 days of the last dose of investigational product of the active period or re-treatment period, this event is not a treatment-emergent event.

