5.6. General Adverse Events

The occurrence of all treatment-emergent adverse events (excluding infection and ISR), infections, infections considered preventable by vaccination, and injection site reactions will be separately summarized by incidence rate (proportion of subjects reporting events) and adjusted rate per 100 subject-years of exposure to etanercept. Adverse events will also be summarized by severity and relationship to investigational product. Adverse events occurring in >1 subject in any of the subtypes may be summarized as well.

- Tabulations of withdrawals from investigational product due to adverse events will be provided.
- In addition to showing cumulative rates over the entire study period (including both parent study and extension), incidences of subjects with treatment-emergent event as well as exposure-adjusted event rates will also be categorized by year for each year from 1 through 10.

These summaries will be performed for FAS (treatment-emergent events in on-drug period (active and retreatment periods together)) and WAS.

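### The SAP counts adverse events to 30 days after the last dose, but for subjects who stop early and enter observation the protocol stops collecting most non-serious events at the early withdrawal visit

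*Protocol*

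**What the plan says.** **Analysis rule.** On non-serious events, SAP 4.2.2 states: "Adverse events that occur up to 30 days after the last dose of investigational product will be counted as having occurred during the treatment period". It adds: "This is applied for active and retreatment periods". SAP 5.2 defines treatment-emergent events as those "with onset dates between the first dose date of investigational product and within 30 days after the last dose of investigational product". Neither section requires the subject to be on drug at Month 96. Both exclude an event that begins in observation only if it begins more than 30 days after the last dose, so an earlier one is meant to count. SAP 5.6 carries the definition into the tables: "These summaries will be performed for FAS (treatment-emergent events in on-drug period (active and retreatment periods together)) and WAS".

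**Collection rule.** Protocol 8.2 records all adverse events to the last visit of the active or withdrawal/re-treatment period. It then continues "for 30 days after the last dose of investigational product for those subjects who are in either the active treatment period", and the rest of the sentence adds the re-treatment period and the condition of being there at Month 96. The Section 6.1.3 follow-up visit collects "Adverse events, including malignancies, serious adverse events, infections, medically important infections, and injection site reactions", but only from subjects still receiving drug at about Month 96.

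**After an early stop.** Section 6.1.4 requires an early withdrawal visit, at which all adverse events are taken. For a subject who then enters observation, footnote u of the active-treatment schedule limits recording: "For subjects in the observational period, only serious adverse events, malignancies and medically important infections". Footnote f says that "the first observational visit will occur at the study site and will be scheduled 30 days" (± 7 days) after the early withdrawal visit. The content list in Section 6.1.6 for that visit contains no general non-serious adverse events.

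**The concern.** The analysis window is wider than the collection window for one group of subjects. Following both documents as written, the treatment-emergent tables would count post-dose events for subjects on drug at Month 96 and for those who move into the withdrawal period. They would miss most non-serious ones for subjects who move into observation. An absent event in that stretch would look the same as an event that did not happen.

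The long-term safety profile is a secondary objective, and SAP 5.6 reports these events as percentages and exposure-adjusted rates, cumulatively and by year. The stake is whether those figures mean what the SAP's definition says they mean.

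**Working it through.** The plan gives no figure to reproduce: enrolment of about 100 is not derived from a calculation. The check compares the two rules by route off drug and then sizes the gap.

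**1. Rules side by side (non-serious events other than malignancies and medically important infections).**

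| Route | SAP window after last dose | Protocol collection | Gap |
|---|---|---|---|
| On drug at Month 96 | 30 days | to 30 days after last dose (8.2, 6.1.3) | none |
| Stops early, enters withdrawal period | 30 days | all events while in that period (8.2; withdrawal schedule, footnote t) | none |
| Stops early, enters observation | 30 days | to the early withdrawal visit (6.1.4, 6.1.6, 8.2) | that visit to day 30 |

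**2. Length of the gap.** Let d be the days from last dose to the early withdrawal visit. The documents do not fix d; Section 6.1.4 only asks for a prompt visit once stopping is decided. Gap = max(0, 30 − d) days; divide by 365.25 for years.

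| d (assumed) | Gap, days | Share of window | Years per subject |
|---|---|---|---|
| 0 | 30 | 100% | 0.082 |
| 7 | 23 | 77% | 0.063 |
| 14 | 16 | 53% | 0.044 |
| 21 | 9 | 30% | 0.025 |
| 30 | 0 | 0% | 0 |

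**3. Total unobserved time.** The number k of early stoppers entering observation is not given. For assumed k = 25, 50, 75 of about 100, k × gap / 365.25 is 2.1, 4.1 and 6.2 subject-years at d = 0, and 1.1, 2.2 and 3.3 at d = 14.

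**4. Events missed per 100 such subjects.** Formula: 100 × gap / 365.25 × rate / 100, with assumed rates of 50 to 400 non-serious events per 100 subject-years.
- d = 0: 8.21 subject-years, so 8.21 × 0.5 = 4.1 to 8.21 × 4 = 32.9 events.
- d = 14: 4.38 subject-years, so 2.2 to 17.5 events.

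**5. Scale.** If 100 subjects each had 96 weeks of parent-study exposure, that is 100 × 672 / 365.25 = 184 subject-years. Fifty subjects with the full gap lose 4.1, and 4.1 / 184 is about 2%. At equal event rates the share of events lost is of that order, and smaller once extension exposure is added.

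**6. Effect on the rates.** SAP 5.11 sets exposure as (last dose date − first dose date + 1) / 365.25, and SAP 5.5 defines the adjusted rate as events / exposure × 100. The post-dose days are in no one's denominator. A Month 96 completer's tail events enter the numerator with no added exposure; corresponding events in an observation entrant do not enter at all. The pooled rate therefore mixes two ascertainment rules.

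**The case against.** The strongest case against is that little is lost. The event that led to stopping is taken at the early withdrawal visit, and Section 6.3 asks for follow-up of unresolved events. Only new, non-serious, not medically important events between that visit and day 30 are missed, in descriptive tables without a control group. All of that stands, and it sets the size of the point.

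Two passages might be read as closing the gap. The schedule says adverse events are collected through 96 months, and 8.2 refers to collection until early withdrawal from the study. The first is narrowed by period in footnotes t and u; the second ends collection for active-period subjects and adds no 30 days.

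A reader might also infer more than the documents support:
- *That the loss depends on why the subject stopped, or falls on those most prone to post-dose events.* It depends on the period entered next. Early stoppers who enter the withdrawal period keep full collection, and nothing in the documents shows that observation entrants have more post-dose events.
- *That the whole 30 days is lost.* That is the ceiling, reached only if the early withdrawal visit is on the last-dose day.
- *That the adjusted rates are too low in absolute terms.* They are low only against the SAP's own numerator. Completers' tail events, counted without exposure, push the other way.
- *That injection site reaction rates are materially affected.* New reactions are unlikely once injections stop, and earlier ones are recorded at the early withdrawal visit.

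The re-treatment schedule appears to mark adverse events at the Month 96 follow-up visit with its observational footnote, against Section 6.1.3. Other marks in that row are garbled in the text available, so this is at most a clerical item.

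**Conclusion.** The mismatch holds. For subjects who leave drug early and enter observation, the SAP counts a class of events that the protocol does not collect between the early withdrawal visit and day 30. The result is a small under-count in the general treatment-emergent and non-serious infection tables, relative to the SAP's definition, and rates that pool two ascertainment rules.

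The wording conflict is certain. Its numerical size is not: it rests on assumed visit timing, event rates and numbers of early stoppers, and is plausibly around 2% of events or less. The primary endpoint, serious adverse events and medically important infections are collected in every period and are untouched. The point is limited to the extension, because the parent study's collection rules are not in these documents. It is worth correcting because the correction is cheap, not because conclusions depend on it.

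**What to change.** **Preferred: amend the protocol.** In 8.2, 6.1.6 and the schedule footnotes, require all adverse events to be recorded through 30 days after the last dose for every subject who stops investigational product in the active or re-treatment period, whichever period comes next. The existing on-site first observational visit can serve. It falls 23 to 37 days after the early withdrawal visit, so if that visit is on the last-dose day it could come up to 7 days before the window closes (30 − 23). The rule should therefore be tied to day 30 after the last dose, with a later check where needed.

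The cost is slightly more adverse event entry, and possibly a change to the observational consent text, since Section 6.1.4 gives that period its own consent. Observation is optional, so subjects who decline it remain uncovered; report their number.

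**Otherwise: amend the SAP.** In 4.2.2 and 5.2, end the non-serious treatment-emergent window at the early withdrawal visit for subjects who enter observation. State the under-ascertainment in the table notes and the study report. This costs a few lines of text but leaves the two rules different by route.

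**In either case,** reconcile the adverse event footnote on the re-treatment follow-up visit with Section 6.1.3, after checking the original layout.
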